Rationale for control condition: We wish to implement a low intensity form of dietary intervention as an active placebo, by providing published material on “healthy living” diet to both groups. In general, counseling has very modest effects on body weight, if any. For example, Noda and colleagues⁹¹ examined weight loss over 8 weeks among participants who initially received 30-60 minutes of dietary counseling (n=44) vs. no counseling (n=47). Whereas the dietary counseling group showed modest weight loss (-0.6 kg) compared to baseline and weight in the no counseling group did not change (0 kg), there was no overall significant effect of Intervention Group. Six months of intensive dietary counseling, defined as weekly consultation for the first month and biweekly thereafter, led to modest weight loss (-2.5 kg)⁹² – in this study, we will implement a much less intensive form of dietary counseling. Therefore, dietary counseling alone is not an effective way for achieving weight loss. By contrast, Harvie et al.⁴⁰ found that 8 weeks of 5-2 CR led to a reduction of 6.5 kg. In addition to providing an active placebo, implementing the same dietary counseling to both groups, we intend to make the 5-2 CR group’s diet during non-CR days less variable and similar to that of the “Healthy living” group. Finally, by offering an intervention to control subjects, we intend to increase their motivation for completing the study. Counseling is routinely used as a control in studies implementing behavioral interventions, such as diet and exercise.⁹³

Although, we do not wish to implement detailed dietary counseling besides providing subjects with published material and reviewing it with them, the study Investigators have received advice by long-time collaborator at the US Department of Agriculture’s Beltsville Human Nutrition Research Center [name]. The Center is specialized in testing novel dietary interventions and implementing comprehensive behavioral interventions to ensure compliance. Study investigators and the Clinical Research Coordinator have become acquainted with their methods and will continue to consult with them throughout this study whenever applicable. The Clinical Research Coordinator or the PI will review the informational materials with participants and provide any necessary clarifications.

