4.a.2. Compliance: We will assess and reinforce diet compliance with correspondence by telephone or electronic mail on week 1, 3, 5 and 7, as well as with Compliance Visits on weeks 2, 4, and 6. To assess compliance during Compliance Visits, we will be measuring plasma β -hydroxybutyrate. Values around 2-2.5 μ M/mL during CR days suggests compliance during 5-2 CR. β -hydroxybutyrate values of 0.5-1.0 μ M/mL suggest non-compliance with 5-2 CR, but would be expected for non restricted days and for the

control group.³⁹ In addition, we will be measuring body weight. Weight loss for 5-2 CR is expected to be about 2% per week based on our previous work.³⁹ Therefore, a progressive decrease seen after 2 weeks of 5-2 CR and persisting in the 5-2 CR group over 8 weeks suggest compliance to 5-2 CR,³⁹ while a smaller decrease in body weight is expected for the control group.

In addition, we will contact participants by telephone or electronic mail (using the Secure Email & File Transfer Service: <https://secureemail.nih.gov/bds/Login.do>) weekly to assess not only compliance with the diets, but also mood, level of energy, difficulty concentrating, headaches, feeling cold, constipation, negative emotions (sadness/depression, anxiety, irritability), hunger and preoccupation with food.^{39,40,94} For e-mail communications, we will provide participants with the web-address of the Secure Email & File Transfer Service with instructions on how to acquire login credentials.

4.b. Recruitment

Participants may be recruited through direct advertisement. Brochures and flyers will be used. Recruitment letters may be mailed to health care providers and to those participants who have requested information. We may place ads and/or public service announcements (PSA) on websites, in radio broadcasts, television, as well as newspapers, newsletters, and magazines. Direct mailing through established marketing and advertising organizations might also be used. Pre-screening over the telephone will utilize the eligibility checklist. Participants that we believe are likely to be eligible will come to the NIA-Clinical Research Unit to undergo screening.

We anticipate an accrual rate of 2-6 participants per month.

4.c. Screening

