This visit will occur within four weeks from the Screening Visit. Participants will arrive on the NIA-Clinical Research Unit after a 12-hour fast. The following procedures will be done: vital signs, anthropometric measurements (weight, waist circumference, sagittal diameter), and a blood draw for clinical labs (CBC, PT, PTT, and INR to ensure safety of the LP), urine pregnancy test (only in women who are able to become pregnant), and research labs including DNA collection (for APOE genotyping and gene expression studies). A 4-hour mixed meal tolerance test will be done. They will also have cognitive testing and will be asked to complete the Symptoms Review Questionnaire, PANAS, and RAND SF-36. A lumbar puncture (LP) will take place; up to a total of 15 mL of CSF will be collected. Participants will have a brain MRI. About 168 mL of blood will be taken during the visit. To facilitate scheduling or satisfy a given participant's request, we may split the various procedures of the Baseline Visit over two days within a week from each other.

4.d.3. 5-2 CR or control groups

At the end of the Baseline Visit, all participants will receive informational materials and one-on-one dietary counseling about "healthy living", consisting of providing and reviewing published material (by the CDC and USDA) on meal portion control, calories in common beverages, meal substitutions for controlling calorie intake, and other dietary considerations. Participants will then be randomized by study investigators into one of two groups to either 1) implement 8 weeks of 5-2 CR (cases); or 2) implement "healthy living" diet (controls).

Participants in the 5-2 group will receive all shakes (Boost®, CWI Medical) from the NIA-Clinical Research Unit.

4.d.4. Compliance visits

To assess and reinforce compliance with their respective diet, we will contact participants by phone or email (via the Secure Email & File Transfer Service: <https://secureemail.nih.gov/bds/Login.do>) at weeks 1, 3, 5, 7 and four days after the Outcome Visit. In addition, we will conduct 2, 4, and 6 week Compliance Visits. The same procedure described below will occur during each one of these.

These visits will take place during the second of the two consecutive restriction days for the 5-2 CR group or any day for the "healthy living" diet group after an 8 hour fast. A blood draw to measure β-hydroxybutyrate, vital signs and anthropometric

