4-hour mixed meal tolerance test: After fasting for at least 12 hours, participants will be asked to drink 5 mL/Kg of the dietary supplement shake Ensure Plus®. Ensure Plus® is a mixed liquid meal; one bottle (480 mL) contains 95 g carbohydrate as dextrose, 26 g protein, and 25 g fat, providing 710 kilocalories. In addition, to inducing a change in glucose and insulin, the mixed meal tolerance test is ideal for testing changes in GLP-1, GIP, ghrelin, glucagon, pancreatic polypeptide, C-peptide, and other hormones. A blood draw will take place before subjects consuming the liquid meal. Plasma, serum and whole blood biomarkers will be measured from this blood draw. for biomarkers, hormones, and cytokines (approximately 35 mL). Then subjects will ingest the liquid meal, followed by blood draws every 20 minutes (5 mL per sample). Typically, participants will have an intravenous (IV) line placed in an arm vein for blood draws.

Lumbar puncture (LP): Participants will have LPs performed during the Baseline Visit and Outcome Visit at 8 weeks, to provide CSF for measurement of biomarkers. Up to a total of 15 mL of CSF will be collected on each of those two visits. CBC, PT, and PTT results should be available prior to each LP taking place. Participants will be encouraged to be well hydrated on the day of the LP.

In individuals in whom a landmark-guided LP at the bedside is deemed technically difficult by the medical staff (such as in the presence of degenerative lumbar spine disease, prior lumbar spine surgery, kyphosis/scoliosis or other conditions) or fails, a licensed Interventional Radiologist may perform the procedure under ultrasound or X-ray guidance (fluoroscopy-guided LP).

Cognitive testing: Logical Memory and CVLT will be administered using standard procedures. The MMSE will be administered only during the Screening Visit. In addition, we will administer EXAMINER, a software program (<http://examiner.ucsf.edu/index.htm>) implementing a battery of neuropsychological tests that reliably and validly assesses domains of executive function. This software was kindly given via a technology transfer request from [name] at the University of California – San Francisco. We will assess working memory, inhibition, set shifting, fluency, planning, insight, and social cognition and behavior. Neuropsychological testing will take approximately 1 hour to complete.

Brain MRI: In total, structural MRI, fMRI and MRS will last about 2 hours.

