The goal of this study is to provide proof of concept that 5-2 CR compared to dietary counseling can lower IR and ameliorate any detrimental effects on middle to older age cognitive performance, brain metabolism and function and normalize any biomarker abnormalities associated with higher risk of AD. Children do not develop AD, and there are no data to suggest that IR during childhood may impact future AD risk. In addition, 5-2 CR in juvenile animals permanently stunts their physical growth. Children are, therefore, not an appropriate population to examine for the purposes of our study.

11. c. Justification for exclusion of other vulnerable participants

If the present study provides proof of concept that 5-2 CR compared to dietary

counseling improves cognitive performance, brain metabolism and function and normalizes biomarker abnormalities associated with higher risk of AD, it would “pave the way” for testing it in cohorts with age-related cognitive impairment or AD. The study requires following strict instructions for 5-2 CR diet, which participants with cognitive impairment would find hard to follow. In addition, this is a proof of concept study that involves more than minimal risk without direct benefit. The study involves some minor but real discomfort (e.g. feeling hungry) and invasive procedures (such as LP), which are not appropriate for those without consent capacity in this study.

11. d. Justification of sensitive procedures

The experimental paradigm does not involve the use of deception, or other sensitive procedures.

11. e. Safeguards for vulnerable populations

We will perform pregnancy tests and exclude pregnant (and nursing) women.

11. f. Qualifications of investigators

The Principal Investigator has verified that all individuals working on this protocol required to take HRPP training under OHSRP SOP 25 (Training requirements for the NIH Human Research Protections Program) have completed all required training.

[name]. (LCI/NIA)

[name] is a Board-certified neurologist with subspecialty training on dementia and Experimental Therapeutics in Neurology. He will be principal investigator and medically responsible investigator of the protocol. He has been primarily responsible for the design of the study and will oversee the project, ensure quality assurance of the data and analyze the data. He will obtain consent, conduct History and Physicals and perform LPs.

[name]. (LNS/NIA)

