[name] is a Senior Research Fellow in the Laboratory of Neuroscience. She has completed her post-doctoral training in Neurosciences at University of California Los Angeles. She is also a licensed Nurse Practitioner and has practiced as a NP in the Johns Hopkins Neurology. [name] will be lead investigator on the protocol. She will be responsible for multiple clinical duties along with PI including overseeing participants' safety. She will obtain consent, conduct History and Physicals and perform LPs.

[name], MA, Ph.D. (LNS/NIA)

[name] is a Postdoctoral Fellow in the Human Neuroscience Unit under the training of [name]. He will be responsible for recruitment and contact with participants,

cognitive testing, MRI/fMRI/MRS, and data analysis. [name] has over 5 years of experience with neuropsych assessment and MRI research on patients with neurodegenerative diseases

12. Anticipated benefit

This pilot study of two short-term diets is not expected to generate direct benefits for the participant. While the diets are likely to decrease body weight and increase insulin sensitivity (i.e., decrease HOMA-IR), changes which may be desirable to the participants and their physicians, the changes are likely to be temporary. This is a short-term study and, therefore, the magnitude and duration of these effects and their impact on long-term health is unclear. The study will generate generalizable knowledge on the effects of short-term implementation of 5-2 CR.

13. Classification of Risk

13. a. For adults

Overall, we classify the study as greater than minimal risk.

13. b. For adults without consent capacity

Not applicable.

13. c. For children

Not applicable.

13. d. Overall risk and benefit consideration

The risks are reasonable in relation to anticipated benefit.

14. Consent Documents and Process

14. a. Designation of those obtaining consent

The principal investigator, clinical research coordinator (nurse) and NIA research nurses and nurse practitioners will be authorized to obtain consent. Investigators identified as being authorized to obtain consent in section 11.f. above will be allowed to obtain consent. In addition, NIA research nurses and nurse practitioners are qualified to obtain consent by their training and will also be authorized to obtain consent. All staff obtaining informed consent has completed the NIMH HSPU "Elements of Successful Informed Consent" training.

14. b. Consent procedures

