ATTACHMENT E. Symptoms Review Questionnaire for 5-2 CR participants

Symptoms Review Questionnaire

Intermittent Calorie Restriction

Since **last week**, on a 1-10 scale, please rate how you felt on **NON-CR DAYS** for:

	Less	→	More								
Amount of Energy	0	1	2	3	4	5	6	7	8	9	10
Ability to Concentrate	0	1	2	3	4	5	6	7	8	9	10
Constipation	0	1	2	3	4	5	6	7	8	9	10
Headache Severity (if any)	0	1	2	3	4	5	6	7	8	9	10
Feeling Cold	0	1	2	3	4	5	6	7	8	9	10
Feeling Sad/Depressed	0	1	2	3	4	5	6	7	8	9	10
Feeling Irritable	0	1	2	3	4	5	6	7	8	9	10
Feeling Anxious	0	1	2	3	4	5	6	7	8	9	10
Feeling Hungry	0	1	2	3	4	5	6	7	8	9	10
Preoccupation with Food	0	1	2	3	4	5	6	7	8	9	10

Since **last week**, on a scale from 1-10, please rate how you felt on **CR DAYS** for:

	Less	→	More								
Amount of Energy	0	1	2	3	4	5	6	7	8	9	10
Ability to Concentrate	0	1	2	3	4	5	6	7	8	9	10
Constipation	0	1	2	3	4	5	6	7	8	9	10
Headache Severity (if any)	0	1	2	3	4	5	6	7	8	9	10
Feeling Cold	0	1	2	3	4	5	6	7	8	9	10
Feeling Sad/Depressed	0	1	2	3	4	5	6	7	8	9	10
Feeling Irritable	0	1	2	3	4	5	6	7	8	9	10
Feeling Anxious	0	1	2	3	4	5	6	7	8	9	10
Feeling Hungry	0	1	2	3	4	5	6	7	8	9	10
Preoccupation with Food	0	1	2	3	4	5	6	7	8	9	10

Have you experienced any other symptoms that you did not have before going on the diet? If so, please write down those symptoms here:

Participant ID: _____

Investigator/Staff Name: _____

Date: _____

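### One investigator holds participant contact, cognitive testing, imaging and data analysis, and no masking of tester, image processing, assay or analysis is stated

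*Combined protocol and SAP*

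**What the plan says.** Section 11.f says of one postdoctoral investigator: "He will be responsible for recruitment and contact with participants". The same sentence adds "cognitive testing, MRI/fMRI/MRS, and data analysis". The PI, in the same section, is also to "ensure quality assurance of the data and analyze the data", while conducting physical examinations and lumbar punctures.

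On allocation, section 4.d.3 states: "Participants will then be randomized by study investigators into one of two groups". On contact, section 4.a.2 has the study team reach participants "weekly to assess not only compliance with the diets" but also mood and symptoms. Attachment E holds two forms, one of them headed "Symptoms Review Questionnaire for 5-2 CR participants", which asks separately about restricted and unrestricted days. Table 1 schedules this questionnaire at the Outcome Visit.

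On testing, section 4.d.6 says "Logical Memory and CVLT will be administered using standard procedures", and section 8.a has investigators giving both questionnaires and cognitive tests. On diet material, section 4.a.1 says: "The Clinical Research Coordinator or the PI will review the informational materials with participants and provide any necessary clarifications".

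No available section provides for a masked tester, masked image processing, a masked assay or a masked analyst.

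**The concern.** Participants in a diet trial cannot be masked, but the people who test them, process their scans and analyse their data can be. Here one person has contact with participants and then carries out each of those steps. Contact that concerns diet reveals the arm, and so does the arm-specific symptom form.

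Verbal memory tests leave room for prompting, pacing and scoring judgement. Imaging pipelines leave room for choices on exclusions, motion and fit quality. Section 1 predicts better cognition with 5-2 CR, and section 10.a uses one-tailed tests without multiplicity correction for secondary outcomes. A drift toward the hypothesis would therefore fall in the rejection region. Section 10.a also says that the data are meant to inform later studies, so an inflated cognitive effect would carry forward into their design.

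**Working it through.** **What the documents establish about knowledge of the arm**

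| Point | Where | Status |
|---|---|---|
| One person has contact, cognitive testing, imaging and analysis | 11.f | Stated |
| Investigators randomize | 4.d.3 | Stated |
| Regular contact covers diet compliance | 4.a.2, 4.d.4 | Stated, but the caller is not named |
| Symptom form differs by arm | Attachment E | Stated |
| Tester knows the arm | none | Inferred from the rows above and the absence of masking |

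Section 4.d.3 places randomization at the end of the Baseline Visit, while section 4.d.1 lists it before that visit. Baseline testing may therefore precede allocation, and the exposure is clear only at the Outcome Visit.

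**Inputs for the size**

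- 20 per arm (10.b); alpha 0.05 for non-MRI analyses and one-tailed tests (10.a).
- Cognition: f = 0.4, stated power 0.81 (10.b). For two groups d = 2f = 0.8.
- Correlation between repeated measures 0.4 (10.b, given for the primary outcome; carrying it over to cognition is my assumption).
- Shift due to knowledge of the arm: 0.1 to 0.4 SD. This is an assumption; the documents give no such figure.

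**The plan's own figure**

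Noncentrality = d × √(n/2) = 0.8 × √10 = 2.530. One-sided normal power = Φ(2.530 − 1.645) = 0.81, which reproduces the plan. The noncentral t with 38 df gives 0.80. Splitting roles changes neither the sample size nor this power.

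**False-positive rate with no true effect and a shift b toward 5-2 CR**

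The rate is P(T > 1.686), where T is noncentral t with 38 df.

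- Shift in SD of change: noncentrality = b × √10.
- Shift in Outcome-score SD: SD of change = √(2 × (1 − 0.4)) = 1.095, so noncentrality = (b / 1.095) × √10.

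| b | Rate, b in SD of change | Rate, b in Outcome-score SD |
|---|---|---|
| 0 | 0.050 | 0.050 |
| 0.1 | 0.091 | 0.087 |
| 0.2 | 0.153 | 0.141 |
| 0.3 | 0.238 | 0.214 |
| 0.4 | 0.344 | 0.305 |

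**Two checks on reach**

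- At the fMRI voxel threshold of 0.005, b of 0.1 to 0.4 SD of change gives 0.012 to 0.086, before cluster correction. The table must not be read across to imaging.
- A two-sided test at 0.05 gives 0.061 to 0.234 for the same shifts. One-tailed testing worsens the problem but does not create it.

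**The case against.** The strongest reply is that several links are inferred.

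- **Calls and scoring.** A reader might infer that this investigator makes the weekly diet calls and scores the tests. The documents do not say so. The contact sections speak of the team, section 4.e gives the post-Outcome contact to an investigator or nursing staff, and nobody is named as scorer. Review of the diet material already lies with the coordinator or the PI.
- **Incomplete roster.** Part of section 11.f is not in the available text, so other testers or analysts may be described there.
- **Reach.** A reader might take the point to undermine the primary outcome or every secondary one. The primary is a laboratory exosomal ratio, and no section says this investigator runs the assay. Stored samples carry codes, although the study team holds the link. EXAMINER is computerized. MRS fitting uses ProFit with Cramer-Rao bounds, and regions of interest and thresholds for fMRI are named in advance. Section 9 calls all secondary outcomes exploratory.
- **Feasibility.** Among the roles visible, only this investigator has stated neuropsychological assessment experience, and no staffing capacity is given. The documents therefore do not show that the change needs no extra effort. The Outcome Visit falls on a restriction day for 5-2 CR (sections 4.d.1 and 4.d.5 differ on which one) and lasts 7 to 9 hours, so participants may reveal their arm.

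All of this narrows the point. It does not remove it: the combined role is stated, the masking is absent from the available text, and section 1 lists cognitive performance and imaging among its main outcomes. An open diet explains unmasked participants; it does not explain an unmasked tester or analyst.

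**Conclusion.** The point holds in limited form. The plan concentrates contact, testing, imaging and analysis in one role and states no masking, so knowledge of the arm is likely, though not documented, for Logical Memory and CVLT at the Outcome Visit and for image processing. The exposure is mainly to exploratory secondary outcomes.

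For the cognitive tests, the illustrated rise in one-tailed type I error is from 5% to 9-34%, or 9-30% if the shift is expressed in Outcome-score SD. Both ranges rest wholly on the assumed 0.1 to 0.4 SD shift, and the second also on a correlation of 0.4. They show sensitivity and do not estimate bias in this trial. The change is worth making because it is cheap relative to the protection it gives.

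**What to change.** - **Diet contact.** Assign counselling, shake dispensing, compliance calls and Compliance Visits by name to the coordinator, the nurses, the nurse practitioner or the PI. The PI also analyses data, so the coordinator and nurses are the better first choice.
- **Testing.** Keep the cognitive tester free of diet contact and of the arm-specific symptom forms. Ask participants not to mention their diet at Outcome testing.
- **Processing and analysis.** Process MRI and MRS, run the exosome assays and finalize analysis scripts under coded A/B labels. Withhold weight and ketone data until processing is complete, because they could decode the labels.
- **Reporting.** State in sections 4.d and 10.a who is masked, to what and until when.

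The cost is some rescheduling of existing duties and the handling of a code list. Visits, sample size and power are unchanged. Masking will be partial, because participants may reveal their arm and the Outcome Visit falls on a restriction day for 5-2 CR.
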